10.1. Adverse Event Preferred Term and Body/Organ System Summary Tables

TEAEs will be summarized by SOC and PT by dosing group. For a given event, a subject will be counted once for the subject count, if the subject reported one or more of the same events. Each event will be counted separately for the number of events.

10.1.1. Summaries of Adverse Event Incidence Rates for All Subjects

Not applicable.

10.1.2. Missing and Partial AE Onset Dates

See Section 6.8.3

10.1.3. Summaries of Adverse Incidence Rates for Serious Adverse Events (SAE), Adverse Event Dropouts, and Death

SAEs will be listed.

10.2. Total Duration of Therapy, Average Daily Dose, Maximum Daily Dose, Final Daily Dose of Study Medication, and Compliance

The duration of exposure (Days), within a dosing group, is calculated as follows:

• Duration of Exposure (Days) = the later of (the last date returned or final treatment end date) minus the treatment start date+1.

The Total duration of exposure (Days) is computed as the sum of the individual study drug durations across dosing groups.

Descriptive statistics will be presented for the duration of exposure (in days) by dosing group. The following duration of exposure categories will also be summarized by dosing group: at least 1 day, at least 7 days, at least 14 days, at least 28 days, at least 56 days, at least 84 days, at least 112 days, and at least 140 days.

Drug compliance for each study visit is captured in eCRF.

Study treatment exposure and drug compliance data will be listed.

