An optional serial PK/PD substudy was to include subjects who provided consent to evaluate the PK and PD of BCX9930 at the Day 1 Visit and/or at a subsequent visit prior to the Week 24 Visit. Serial sampling of urine and blood was to be performed over a period of 6 hours. Subjects who did not participate in the Baseline (Day 1) PK/PD sample collection were eligible to participate at a subsequent clinic visit prior to the Week 24 Visit.

All subjects were to have a single blood sample drawn for PK analysis at each clinic visit ("sparse sampling" to support PPK and PK/PD modeling). For subjects participating in the serial PK/PD substudy, a single blood sample was to be drawn for PK and PD analysis at visits where serial blood samples were not collected through post dose.

All subjects who signed a separate informed consent (optional) were to participate in exploratory pharmacogenomics testing at a single visit from Day 1 up to the Week 24 Visit (including the safety FU Visit, if applicable).

Figure 1: Study Schema by Protocol Version

Protocol Version 3.0

Screening*							500 mg BCX9930 BID ^{‡ ‡}								F			
Weeks	-8		1	2	4	8	12	16	20	.+ 24	28	32	36	40	44	48*	52	54 [∓]
Days	-56	1	8	15	29	57	85	113	141	169	197	225	253	281	309	337	365	-

^{* =} Kidney Biopsies: A screening biopsy may be waived with approval of central pathologist and agreement with the medical monitor for any subject with a prior biopsy ≤ 30 days prior to screening and ≤ 90 days prior to screening for adolescents with C3G.

Subjects with C3G will undergo a percutaneous needle biopsy of the kidney at the Week 24 Visit or within 7 days after the visit. The Week 24 biopsy procedure is optional for adolescent subjects with C3G.

Subjects with IgAN will undergo a percutaneous needle biopsy of the kidney at the Week 36 Visit or within 7 days after the visit.

Subjects with PMN will undergo a percutaneous needle biopsy of the kidney at the Week 48 Visit to within 3 days after the Week 52 Visit. Dosing with BCX9930 will continue until the Week 52 Visit or until the day of the biopsy procedure.

[figure not shown]
+ = Clinical Benefit Assessment

T = Follow-up/End of Treatment Visit: 14 ± 3 days after last dose of BCX9930 for all subjects

= Safety Follow-up Visit: 28 ± 3 days after last dose of BCX9930 for subjects who discontinue BCX9930 dosing prior to the Week 52 Visit
 F= Follow-Up

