7.1. Treatment group Descriptors

There were only 3 screened subjects who had historical C3G in this study. Two of them had confirmed C3G per central pathologist and started BCX9930 under 500 mg BID. The unconfirmed C3G subject was a screen failure. No subjects were enrolled under the other two cohorts (IgAN and PMN).

Disposition summaries will be presented by the 'C3G' cohort and all screened subjects.

Demographics and baseline characteristics summaries will be presented by the 'C3G' cohort. All other summaries will be presented by the following dosing groups:

- C3G 500 mg BID
- C3G 500 mg Total Daily Dose
- Total All Doses (Efficacy summaries will not have this column).

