10.3. Concomitant and Other Medications

Any medication that was ongoing, started, or ended on or after the initiation of study drug will be considered concomitant. Concomitant medications will be summarized by dosing groups.

For the subject who received study drug under two different dosing groups, medications taken on or after the initiation of study drug in the first dosing group through one day before the start of the second dosing group will be considered concomitant medications for the first dosing group. Medications taken on or after the start of the second dosing group will be considered concomitant medications for the second dosing group.

Concomitant medications will be listed.

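### SAP 10.2 ends exposure at the later of drug return and treatment end, so it can overstate days on drug and, for the one two-regimen subject, count days twice

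*SAP*

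**What the plan says.** SAP 10.2 calculates duration separately for each dosing group, as "the later of (the last date returned or final treatment end date) minus the treatment start date+1". The Total is "computed as the sum of the individual study drug durations across dosing groups". Neither the returned date nor the final treatment end date is defined, and nothing says where one group's exposure stops when the next begins. The results go into Table 14.1.4.1 as descriptive statistics and as cumulative categories with thresholds at 1, 7, 14, 28, 56, 84, 112 and 140 days.

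Two subjects were treated. SAP 7.1 says of the three screened: "Two of them had confirmed C3G per central pathologist and started BCX9930 under 500 mg BID". It also names a second dosing group, "C3G 500 mg Total Daily Dose".

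SAP 10.3 confirms that one subject had both regimens ("For the subject who received study drug under two different dosing groups") and sets a cut-off for that case: medications taken "through one day before the start of the second dosing group will be considered concomitant medications for the first dosing group". That cut-off is written for concomitant medications only.

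**The concern.** Days on drug end with the last dose. The date on which bottles come back is a logistics date that can fall later. If the return date were used only when the last dose date was missing, it would be a reasonable substitute. SAP 10.2 instead takes the later of the two, so a late return overrides a treatment end date that is known.

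The regimen switch adds a second problem. Applying the formula within a dosing group says whose records are used, but it does not limit the return date. If first-regimen bottles come back on or after the day the second regimen starts, the overlapping days enter the first group, the second group and, because the Total is a plain sum, the Total twice. The authors dealt with the same subject in the next section and gave a cut-off there, but not here.

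The report is to focus on safety, and this is its only exposure table. With two subjects, one subject crossing a threshold moves a category by 50 percentage points; in the one-subject group it moves it by 100.

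**Working it through.** The documents give no exposure figure to reproduce. The check is therefore on the rule itself, followed by illustrations on assumed dates.

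**Inputs from the documents**
- Formula, plain sum and thresholds: SAP 10.2.
- Two treated subjects, both started on 500 mg BID: SAP 7.1. One had two dosing groups: SAP 10.3. So n = 2 for 500 mg BID and for the Total, and n = 1 for 500 mg total daily dose.
- Version 3.0 schema (SAP 4.1, Figure 1): "Follow-up/End of Treatment Visit: 14 ± 3 days after last dose of BCX9930 for all subjects", which is 11–17 days; and "Safety Follow-up Visit: 28 ± 3 days after last dose of BCX9930 for subjects who discontinue BCX9930 dosing prior to the Week 52 Visit", which is 25–31 days.

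**1. Off-drug days**

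Let s be the first dose day, e the last dose day and r the return day, with e and r both recorded.
- SAP rule: max(r, e) − s + 1.
- First to last dose: e − s + 1.
- Excess: d = max(r − e, 0). This is zero or positive, never negative.

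Assumed durations, with a return at one of the two schema visits:

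| First to last dose | Return 11–17 days later | Return 25–31 days later |
|---|---|---|
| 45 days | 56–62: now reaches the 56-day category | 70–76: now reaches the 56-day category |
| 60 days | 71–77: no change of category | 85–91: now reaches the 84-day category |
| 150 days | 161–167: no change | 175–181: no change |

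A category changes only if the true duration lies within d days below a threshold, so never from 140 days upward.

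An excess d in one of two subjects moves the mean and the median by d/2. If both returned late, the shift is (d1 + d2)/2. In the one-subject group it is the full d. Since SAP 7.1 implies that the two-regimen subject went from 500 mg BID to 500 mg total daily dose, that subject's late final return would fall in the second group and the Total, not in the BID group.

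**2. Days counted twice**

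Assume regimen 1 on days 1–56 and regimen 2 on days 57–112, with no gap and with first-regimen returns dated separately. True total: 56 + 56 = 112. Days counted twice = return day − switch day + 1, when the return is on or after the switch.

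| Regimen 1 drug returned | Group 1 + group 2 | Total | Days counted twice |
|---|---|---|---|
| Day 56 | 56 + 56 | 112 | 0 |
| Day 57 (switch day) | 57 + 56 | 113 | 57 − 57 + 1 = 1 |
| Day 64 | 64 + 56 | 120 | 64 − 57 + 1 = 8 |
| Day 85 | 85 + 56 | 141 | 85 − 57 + 1 = 29 |

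The two effects add. If final drug also comes back 28 days after the last dose, group 2 becomes 84 and the last three totals become 141, 148 and 169.

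**3. The corrected rule on the same dates**

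Group 1 ends on day 56 and group 2 on day 112, giving 56 + 56 = 112 whatever the return dates. If the subject took a regimen 1 dose in the morning and a regimen 2 dose in the evening of day 57, last dose dates alone would give 57 + 56 = 113. Ending group 1 no later than day 56 restores 112. The cap therefore has to apply to the group's end date in every case, not only when a return date stands in for a missing last dose date.

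**The case against.** The strongest reply is that no error is shown. Both effects need a late return, and the documents give no dose, switch or return dates. The returned date is undefined, so its meaning as a drug return date is a reading. This stands: the point is about what the rule permits, not about a wrong result.

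A reader might infer that the 11–17 or 25–31 days are the expected overstatement. The documents do not support that. The version 3.0 schema shows visits at those times but not that drug was returned at them. The text that does place accountability at follow-up (Protocol 10.4 and 11.3.6, and the SAP's schedule tables) belongs to version 4.0, and the SAP says that all subjects were recruited before that version. The gaps are illustrations, neither estimates nor bounds.

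A reader might also infer that the safety windows are distorted. They do not use the return date: SAP 10 and 10.4 run them to 30 days after dosing. Those windows also state no cut-off at a regimen switch, but that is a separate matter which this change does not touch.

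Finally, the consequence is small. No exposure-adjusted rate is planned. Treatment administration and compliance are listed (16.2.5.1 and 16.2.5.2), and SAP 6.2 requires notes that define derived variables. With two subjects a reader can compare the table with the dosing records. That limits the harm, but a note describing the formula does not correct the number it produces.

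**Conclusion.** The point holds as a minor defect in a derivation. When both dates are recorded, the rule in SAP 10.2 can overstate exposure and cannot understate it. It does so by the number of days between last dose and return and, for the one two-regimen subject, by counting days twice if first-regimen drug came back on or after the switch. If every return fell on or before the relevant last dose, the table is right as planned.

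The actual size is unknown. The conclusion rests on reading the returned date as the study drug return date and the final treatment end date as the last dose in that dosing group. It might be inferred that the end date means the subject's overall end, in which case every second-regimen day would count twice (112 + 56 = 168 in the example above). The SAP does not say so, and its wording ties the calculation to a dosing group. The stronger claim is not made here, though it is a further reason to define the date.

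Only Table 14.1.4.1 is affected. No efficacy, adverse event or laboratory result depends on this formula.

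**What to change.** Replace the definition in SAP 10.2 with the following:
- Within each dosing group, the end date is the last dose date under that regimen. The study drug return date is used only if the last dose date is missing.
- In every case the end date is no later than the day before the next dosing group starts, the convention SAP 10.3 already uses.
- Duration = end date − first dose date + 1.
- Total = the sum of these non-overlapping durations.
- A footnote to Table 14.1.4.1 states that days of interruption within a regimen are counted.

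The cost is one formula, one derivation and one footnote. The last dose date is already needed for the adverse event and laboratory windows, so no new data are required. The downside is that reported exposure may be shorter, and interruption days within a regimen remain in the figure.

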10.3. Concomitant and Other Medications

Any medication that was ongoing, started, or ended on or after the initiation of study drug will be considered concomitant. Concomitant medications will be summarized by dosing groups.

For the subject who received study drug under two different dosing groups, medications taken on or after the initiation of study drug in the first dosing group through one day before the start of the second dosing group will be considered concomitant medications for the first dosing group. Medications taken on or after the start of the second dosing group will be considered concomitant medications for the second dosing group.

Concomitant medications will be listed.

10.4. Routine Laboratory Data

An assessment of drug induced liver injury (DILI) for elevations in liver function tests will be performed. For ALT, AST, total bilirubin and international normalized ratio (INR) within a dosing group, the maximum post-baseline value across a subject's visits (scheduled and unscheduled, out to 30 days post dose) will be determined for each test. The maximum value for each parameter will then be summarized per the categories given below:

ALT/ AST/ ALT and AST/ ALT or AST	Total Bilirubin	INR	ALT or AST and Total Bilirubin
> 1.5X ULN > 3X ULN > 5X ULN > 10X ULN > 20X ULN	> ULN > 1.5X ULN > 2X ULN	> 1.5	ALT > 3X ULN and Total Bilirubin > 1.5X ULN ALT > 3X ULN and Total Bilirubin > 2X ULN AST > 3X ULN and Total Bilirubin > 1.5X ULN AST > 3X ULN and Total Bilirubin > 2X ULN (ALT > 3X ULN or AST > 3X ULN) and Total Bilirubin > 1.5X ULN (ALT > 3X ULN or AST > 3X ULN) and Total Bilirubin > 2X ULN (ALT > 3X ULN or AST > 3X ULN) and Total Bilirubin > 2X ULN)

Within a specific outcome (eg, ALT, AST, etc.), the categories are descending cumulative and not mutually exclusive.

In addition, for serum creatinine, within a dosing group, the maximum post-baseline value across a subject's visits (scheduled and unscheduled, out to 30 days post dose) will be determined. The maximum value will then be summarized by dosing group for the categories given below:

- > ULN but $\leq 1.5 \times$ ULN
- $> 1.5 \times ULN \text{ but } < 3 \times ULN$
- $\geq 3 \times ULN$
- ≥ 0.3 mg/dL increase from baseline.

Laboratory abnormalities will be graded according to CTCAE (Version 5.0, 27 November 2017). Any graded abnormality that occurs following the initiation of study drug (within 30 days post last dose) and represents at least 1-grade increase from the baseline assessment is defined as treatment emergent. A listing of all liver function test results for subjects experiencing a treatment-emergent Grade 3 or 4 liver function test will be provided.

All laboratory data will be listed.

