7.4. Individual and Study Termination Criteria

7.4.1. Study Drug Treatment Discontinuation Criteria

A subject will be permanently withdrawn from BCX9930 for any of the following reasons:

• Pregnancy in a female subject.

^{† =} Clinical Benefit Assessment

T = Safety Follow-up Visit: 28 ± 3 days after last dose of BCX9930 for all subjects

F = Safety Follow-Up

- Emergence of an AE, including a laboratory abnormality, or other unacceptable toxicity that, in the judgment of the investigator, compromises the ability of the subject to continue study-specific procedures or it is considered not to be in the subject's best interest to continue due to an altered benefit-risk profile.
- Intercurrent illness or the emergence of a new medical condition that would, in the judgment of the investigator, affect assessments of clinical status to a significant degree.
- Treatment-emergent alanine aminotransferase (ALT) or aspartate aminotransferase (AST) > 3 × ULN combined with either laboratory abnormalities indicative of significant hepatic toxicity (ie, meeting Hy's law, total bilirubin > 2 × ULN OR with an INR > 1.5) or with symptomatology of acute hepatitis (ie, severe fatigue, nausea, vomiting, right upper quadrant pain and tenderness, fever, rash, and/or eosinophilia [> 5%]) and assessed by the investigator as probably, or definitely related to BCX9930 treatment.
- Treatment-emergent increase in sCr \geq 3 × ULN (confirmed by repeat testing) without any other potential cause of renal dysfunction
- In the investigator's opinion it is in the best interest of the subject to discontinue from further dosing.
- Invasive meningococcal infection or any serious invasive bacterial infection that occurs after BCX9930 is initiated.
- Subject request to discontinue for any reason.
- Subject noncompliance (eg, protocol deviation), as assessed by the sponsor or investigator, to be detrimental to study or subject benefit-risk profile.
- Discontinuation at the request of the sponsor, relevant competent authority, or the governing institutional review board (IRB), research ethics board (REB), or independent ethics committee (IEC) (collectively referred to as "ethics committee").

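### The SAP liver table builds its combined ALT/AST-and-bilirubin rows from separate per-test maxima, so they need not be concurrent, and it has no row for the protocol's ALT/AST-with-INR combination

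*SAP*

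**What the plan says.** SAP 10.4 sets out an assessment of drug-induced liver injury, reported in Table 14.3.2.1. The first step treats ALT, AST, bilirubin and INR one by one, separately by dosing group: "the maximum post-baseline value across a subject's visits (scheduled and unscheduled, out to 30 days post dose) will be determined for each test". A second step fills the table from those values: "The maximum value for each parameter will then be summarized per the categories given below".

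The categories are of three kinds:

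- Transaminase rows: "> 1.5X ULN > 3X ULN > 5X ULN > 10X ULN > 20X ULN".
- Single-test rows for bilirubin, and for INR above 1.5.
- Combined rows such as "ALT > 3X ULN and Total Bilirubin > 2X ULN", with versions for AST, for either enzyme, and for bilirubin above 1.5 x ULN.

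No combined row involves INR.

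Protocol 7.4.1 bases a treatment-discontinuation criterion on ALT or AST above 3 x ULN in combination with other findings. The laboratory part is given as "meeting Hy's law, total bilirubin > 2 × ULN OR with an INR > 1.5". Protocol 13.5.1 repeats the pairing with bilirubin or INR, with exceptions for Gilbert's syndrome and warfarin, and separately names ALT or AST above 8 x ULN.

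The SAP also plans to list all laboratory data, and adds a targeted listing (16.2.8.6): "A listing of all liver function test results for subjects experiencing a treatment-emergent Grade 3 or 4 liver function test will be provided".

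**The concern.** A row that joins an ALT threshold to a bilirubin threshold invites the reader to see a Hy's-law-type pattern, that is, both abnormalities present together. The SAP rule does not test for that. It tests whether each threshold was crossed at some point in the window, perhaps months apart. The protocol's criteria are worded as combinations, so the table and the criteria it appears to report on can disagree.

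The second gap runs the other way. The protocol gives INR the same standing as bilirubin in the combination, but the table separates INR from the transaminases, so that combination cannot be read from it.

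This matters because the abbreviated report is to focus on safety, potential drug-induced liver injury is an event of special monitoring (Protocol 13.1.4), and this is one of only two laboratory summary tables planned (SAP 14.1).

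**Working it through.** The plan states no figure to reproduce. The check applies the SAP rule and a same-sample rule to constructed subjects. The values are illustrative and are not trial data.

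**Inputs.** Per-test maxima, the window and the row definitions come from SAP 10.4. The paired criteria come from Protocol 7.4.1 and 13.5.1. The two treated subjects come from SAP 2, and the dosing groups from SAP 7.1 and 10.3.

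**Rules.** Let A(t) be the higher of ALT and AST, and B(t) total bilirubin, both in multiples of ULN at visit t.

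- SAP row: counted if max A(t) > 3 and max B(t) > 2, each maximum taken separately.
- Concurrent row: counted if A(t) > 3 and B(t) > 2 at the same t.

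If one sample meets both thresholds, both maxima do too. The SAP row therefore contains every same-sample case, and the error can only be an over-count.

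**Case 1: rises apart.** Week 4: ALT 4, bilirubin 0.8. Week 20: ALT 0.9, bilirubin 2.5.

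- SAP: max ALT = 4 > 3 and max bilirubin = 2.5 > 2, so the subject is counted in the combined rows for bilirubin above 1.5 and above 2.
- Same sample: Week 4 fails on bilirubin (0.8) and Week 20 fails on ALT (0.9). Not counted.

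**Case 2: the INR pairing.** Compare two pairs of subjects.

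| Row | One subject with ALT 4 and INR 1.6 together, one normal | One subject with ALT 4 only, one with INR 1.6 only |
|---|---|---|
| ALT or AST > 3 | 1 | 1 |
| INR > 1.5 | 1 | 1 |
| Any combined row | 0 | 0 |

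The rows are identical, but only the first pair contains a subject with the combination. Within one subject, ALT 4 at Week 4 with INR 1.6 at Week 20 also fills the same rows as both at one visit.

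**Case 3: the 8 x ULN cut-off.** ALT 6 and ALT 9 both fall in the rows above 1.5, 3 and 5 and in no higher row, so the table cannot separate them at 8.

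**Window and denominators.** The maximum is taken within a dosing group. Both treated subjects started on 500 mg BID, and SAP 10.3 refers to one who received study drug in two dosing groups. One non-concurrent case in the 500 mg BID column would read 1/2 = 50%. The SAP does not say how the maximum is formed for the all-doses column. If it spans both groups, an ALT peak in one and a bilirubin peak in the other could make a combined case there that appears in neither group column.

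**The case against.** The strongest reply is that this hardly matters. There are two treated subjects, and Listings 16.2.8.1 and 16.2.8.4 will show every chemistry and coagulation result, so a reader can see at once whether the rises coincided. That stands. No information is lost from the report; the weakness is confined to one table.

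It can also be said that any-time maxima are a conservative screen, and that neither document defines how close in time combined abnormalities must be. Both are correct. They support keeping the existing rows, but not leaving them unlabelled.

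A third reply is that Protocol 7.4.1 and 13.5.1 manage individual subjects, depending on relatedness, symptoms, warfarin and Gilbert's syndrome, and that Protocol 14.4.5 does not promise counts of these criteria. This too is fair. It is why the 8 x ULN row and a wider trigger for Listing 16.2.8.6 are optional. The INR pairing differs: the table already reports the bilirubin half of the same either-or criterion.

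Finally, the display specifications in SAP 14.2 are not in the text available, and SAP 6.2 requires notes defining derived variables. A timing rule could sit there. The body of the SAP states none.

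A reader might take Gilbert's syndrome, which the protocol allows at entry, as the main source of false combined cases. The documents do not support that: a persistent bilirubin elevation would coincide with an ALT rise under a same-date rule too, and Protocol 13.5.1 handles it by attribution rather than timing.

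**Conclusion.** The point holds as a matter of labelling and completeness. On its stated rule, Table 14.3.2.1 can over-count, but cannot miss, subjects whose ALT/AST and bilirubin abnormalities occurred in the same sample, and it cannot show the ALT/AST-with-INR combination in the protocol. Practical impact is small for the reasons conceded above.

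Two stronger readings go too far. A reader might infer that the table will report a false liver signal; nothing in the documents says that either subject had any such elevation. A reader might also try to estimate how often unrelated rises would fail to overlap, by counting visits in the Version 4.0 schedule and assuming independent random timing. No subject enrolled under Version 4.0, the timing model would be pure assumption, and the maxima include unscheduled retests. No percentage of that kind is supportable.

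The conclusion assumes that the unseen display specifications add no concurrency condition. It takes no view on which liver thresholds are clinically right; the reporting table and the protocol's criteria need to be reconciled.

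**What to change.** In SAP 10.4 and the shell of Table 14.3.2.1:

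1. Keep the current combined rows, labelled *maxima at any time, not necessarily concurrent*.
2. Add combined rows that require both results on the same sample date, or within a stated number of days: ALT or AST above 3 x ULN with bilirubin above 2 x ULN, and ALT or AST above 3 x ULN with INR above 1.5. A stated window has one practical advantage for INR: the assessment schedule has chemistry but no coagulation at Weeks 3, 5, 6, 7 and 10, so a same-date INR may not exist.
3. State how the maximum and the concurrent rows are formed in the all-doses column.
4. Optionally, add a row for ALT or AST above 8 x ULN, and let the protocol's combined criteria also trigger Listing 16.2.8.6.

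The cost is a few lines of SAP text and programming, with no new data.
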